NEPA has already been shown to significantly improve cardiometabolic risk markers in healthy, sedentary subjects²³, type II diabetes patients²⁴ and obese adults²⁵ and it involves lower intensity physical activities that are probably more feasible than MVPA for PwMS. Moreover, with comparable activity workloads, reducing sitting time by NEPA of longer duration decreases insulin levels and fasting lipid levels more than performing one MVPA bout^{23, 24} that is usually described in current activity guidelines¹⁸. So far however, acute MVPA and NEPA effects on cardiometabolic health in this population have never been described. Therefore, the aim of this study is to investigate whether (1) cardiometabolic health (glycaemic control, blood lipids, inflammation markers and blood pressure) of persons with MS improves when sedentary time is reduced and (2) NEPA results in better cardiometabolic health parameters than (a shorter daily bout of) moderate-intensity exercise when workload of both activities is identical in this population.

2. Methods

A flowchart of the study design is provided in Figure 1. The design of the study, the different activity regimes and the continuous activity monitoring are based on previous research in sedentary subjects²³ and type II diabetes patients²⁴. For practical reasons (subjects are aware of their activity regimen), it is not possible to blind the study. The study is an intervention study with a cross-over design. Participants will follow four regimes of 4 days each including a control, a sit less, a sit and an exercise regime. The order of the sit and sit less regimes will be randomized. Each activity regime will be followed by a wash-out period of 10 days during which subjects will continue their normal lifestyle. Fasting glucose, insulin, inflammation parameters, lipids and blood pressure will be determined at the end of each regime (on day 5).

[figure not shown]

Fig. 1: Flowchart study design. The order of the sit less and sit regime will be randomised. Between each activity regime a wash-out period of 10 days takes place. Abbreviations: d: days, v: visit (v-1,-2: screening visits, v1,3,5,7: attachment of ActivPAL – v2,4,6,12: test days + removing of ActivPAL – v8,9,10,11: exercise sessions)

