2.3. Randomization

At the end of visit -1 subjects will be randomised, if no contra-indications have been observed during the screening. The two below-mentioned schemes (Fig. 2) will be taken into randomisation 15 times. For the last subject the scheme will be chosen randomly

[figure not shown]

Fig. 2: allocation to activity regime schemes.

The randomisation will be done by a member of the research team by drawing a sealed, non-translucent envelop with herein written the scheme. After randomisation, the first activity regime will start within ± 10 days. The regimes will always start on the same day (Saturday) to minimize bias.

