2.4 Regimes

During each activity regime (4 days), participants will be asked to spend 8h sleeping/lying. Subjects will be allowed to sleep \pm 2 hours less or more and replace this sleeping time by sitting (more or less) as long as sleeping time is the same during all regimes. Each activity regime is followed by a wash-out period of 10 days during which subjects can continue their normal lifestyle, but are not allowed to perform more than 60min of MVPA.

Control regime

To provide feedback on how to change activity patterns in order to comply with the subsequent activity regimes, subjects will start with the control regime. This is a baseline measurement of physical activity during which subjects will be instructed not to change activity patterns during these four days and to note all activities they perform.

Sit regime

Here, participants spend 14h of their day sitting, 1h walking and 1h standing. According to the compendium of Ainsworth et al. (2011)²⁷, this corresponds with a daily workload of activities (DWA) of 27 metabolic equivalents (MET's) per day.

Sit less regime

Each day will consist of 3h walking, 4h standing and 9h sitting. These time frames are chosen to result in a comparable DWA increase as the exercise regime compared to the sit regime (+7 MET's)²⁷. The additional 2h of walking and 3h of standing, compared to the sitting regime, will be done in a minimum of four bouts with a time interval of > 1h. The subjects will be instructed to walk on a slow pace. i.e. 2-3 km/h (e.g. walking during shopping and work related walking in an office).

Exercise regime

One hour of sitting in the sit regime will be replaced with 1 training session (1h) on a cycle ergometer in the research center. The remaining hours of each day have to be spent as follows: 13h sitting, 1h walking and 1h standing for daily care. The intensity of the training session (50-60% of W_{max}) results in a DWA of 34.5 MET's according to the compendium of physical activities²⁷. Duration of training sessions will be adapted individually with ActivPAL data of the sit less and sit regime to identically match DWA increase between the sit less and exercise regime, compared to the sitting regime. Details can be found in '3.6 exercise intensity'.

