After an initial resting period of 10min with participants in a supine position in a quiet room with constant temperature (19-21°C), blood pressure (BP) is measured 3 times at 5-min intervals using an electronic sphygmomanometer (Omron®, Omron Healthcare, IL, USA) from the dominant arm and documented as the mean value of the final 2 measurements.

Body weight

Body weight (in underwear) is determined using a digital-balanced weighting scale to the nearest 0.1kg.

4. Statistical analysis

Statistical analyses are performed by IBM SPSS® version 25.0 (IBM SPSS Statistics for Windows, Chicago, IL, USA). Data are expressed as mean \pm SD.

The differences in outcome between regimens are analysed using linear mixed model analyses with activity regimen and period (order of activity regimen) as fixed factors, and an unstructured covariance structure for the four repeated measurements for each person. Shapiro-Wilk test will be used to test normality of the data ($p < 0.05$) and natural log transformations are performed if the outcome is not normally distributed. Likelihood based methods are used for missing values. Numerical variables are presented as mean \pm SD or as medians (first quartile, third quartile) for baseline characteristics (measured during screening) and estimated mean (SEM) for the other values. Regimens are compared pairwise, whereby P-values $\leq 0.05/6$ (Bonferroni correction) are considered statistically significant to account for multiple testing.

The activPAL will be read out and analysed with the activPAL software. The software is able to determine how much time the subjects spent walking, standing and sitting/lying and is also able to estimate energy expenditure (Fig. 1). This makes it possible to objectively determine the proportion of activity/inactivity. We will determine sleeping time based on reported data since the activPAL is not able to distinguish between sitting and sleeping.

5. Data anonymity

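### Control is always period 1 and exercise always period 4, so five of the six planned regimen comparisons, including sit less vs exercise (Aim 2), cannot be separated from time, yet Section 4 treats all six alike

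*Combined protocol and SAP*

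**What the plan says.** Methods (Section 2) describes a cross-over with four regimes and states: "The order of the sit and sit less regimes will be randomized". The other two positions are fixed:

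- **Control is first.** Under Control regime in Section 2.4, "subjects will start with the control regime", so that feedback can be given for the later regimes.
- **Exercise is last.** Table 2 places it on days 43 to 46 for everyone. Sections 2.4 and 2.6 set the length of the cycling sessions from each subject's own sit less and sit recordings, so both must come before it.

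Section 2.3 has two schemes: "The two below-mentioned schemes (Fig. 2) will be taken into randomisation 15 times", and for subject 31, "For the last subject the scheme will be chosen randomly".

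Section 4 specifies "linear mixed model analyses with activity regimen and period (order of activity regimen) as fixed factors", with an unstructured covariance over the four measurements. It then compares the regimens pairwise at 0.05/6. It does not say whether period has four levels or two, and it does not distinguish the randomised comparison from the rest. Aim 2, at the end of Section 1, is the comparison of sit less with exercise at equal workload.

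**The concern.** A cross-over separates treatment from time only where treatments exchange positions. Here only sit and sit less do. Control never leaves period 1 and exercise never leaves period 4, so any change between test days that has nothing to do with the regimen goes straight into comparisons involving either of them.

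Two things are at stake. First, Section 4 can be fitted in two ways. Two analysts following it could reach different models, and one of those models cannot estimate the Aim 2 comparison. Second, where the comparison can be computed, nothing in the plan stops it being presented with the same standing as the randomised one. The 80% power in Section 2.2 then applies to these five only if period effects do not enter them.

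**Working it through.** **Inputs.** Sequences (Sections 2, 2.3 and 2.4, Table 2): control – sit less – sit – exercise, and control – sit – sit less – exercise. From Section 2.2: effect size 0.71, correlation 0.50, two-sided alpha 0.05/6 = 0.00833, power 80%, drop-out 10%, N = 31.

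**The plan's own figure.** With correlation 0.50, the standardised paired difference is 0.71/√(2 × (1 − 0.50)) = 0.71. The exact paired t-test (noncentral t) gives power 0.789 at n = 27 and 0.809 at n = 28. Then 28 × 1.1 = 30.8, rounded up to 31 (28/0.9 = 31.1). The sample size reproduces; the problem is not in N.

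**Reading 1: period as a four-level factor.** Parameters: 1 intercept + 3 regimen + 3 period = 7. The exercise column is identical to the period 4 column, and control to period 1, so the rank is 7 − 2 = 5. Regimens and periods fall into three unconnected blocks: {control, period 1}, {sit, sit less, periods 2 and 3}, {exercise, period 4}. Only comparisons within a block are estimable, which leaves sit less vs sit. Any p-value for the other five depends on an arbitrary constraint.

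**Reading 2: two-level sequence.** Parameters: 1 + 3 + 1 = 5, rank 5, so all six can be computed. With equal sequences and P1 to P4 as the period effects, the period content of each is:

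| Comparison | Period effects carried | Linear drift, in periods |
|---|---|---|
| Sit less vs sit | none | 0 |
| Sit or sit less vs exercise | (P2 + P3)/2 − P4 | 2.5 − 4 = −1.5 |
| Control vs sit or sit less | P1 − (P2 + P3)/2 | 1 − 2.5 = −1.5 |
| Control vs exercise | P1 − P4 | 1 − 4 = −3 |

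With unequal sequences, sit less vs sit picks up (nA − nB)/n of one period's drift: 1/31 = 0.03 at 16/15, and 4/28 = 0.14 at an assumed 16/12. At a drift of 0.2 its type I error is 0.0084 and 0.0090 respectively, so this part is minor.

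**Sensitivity to drift.** The documents give no drift, so these values are assumptions and not a forecast. Drift is linear, in SDs of the paired difference per period; n = 28, 27 degrees of freedom, alpha 0.05/6. Bias is 1.5 × drift for sit less vs exercise and 3 × drift for exercise vs control. Power takes a true difference of 0.71 minus or plus the bias.

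| Drift per period | Type I error, sit less vs exercise | Type I error, exercise vs control | Power, sit less vs exercise, drift opposing | Same, drift favouring |
|---|---|---|---|---|
| 0 | 0.0083 | 0.0083 | 81% | 81% |
| 0.05 | 0.013 | 0.029 | 69% | 89% |
| 0.1 | 0.029 | 0.125 | 55% | 95% |
| 0.2 | 0.125 | 0.63 | 27% | 99% |

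**Properties of the remedy.** Replace period by a term coded −1/2 in period 2, +1/2 in period 3 and 0 in periods 1 and 4. The model has rank 5, all six comparisons can be computed, and the fitted values equal those of Reading 1. The variance of sit less vs sit rises by 1/(1 − ((nA − nB)/n)²): 1.001 at 16/15 and 1.02 at 16/12. A linear visit trend also gives the same fitted values but extrapolates the period 2–3 slope to periods 1 and 4. With equal sequences, variances and correlation, its variance factor is 3.25 for sit less vs exercise and 10 for control vs exercise. An interval √3.25 = 1.8 times wider leaves power at 0.71 of about 25% (22% to 26% at 16/12, depending on which sequence is larger).

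**The case against.** The strongest reply has five parts.

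1. **The order is necessary and disclosed.** This stands, and no change of order is asked for. Disclosure does not separate regimen from period, though.
2. **Control is a baseline and neither aim names it.** This is fair. Aim 1 can be answered by sit less vs sit, which is sound. Of the five affected comparisons, only sit less vs exercise is named in an aim, and the 0.63 above belongs to a comparison outside both. Section 4 nevertheless tests all six.
3. **The protocol already limits drift.** "Each activity regime will be followed by a wash-out period of 10 days"; during wash-out subjects "are not allowed to perform more than 60min of MVPA"; "The regimes will always start on the same day (Saturday) to minimize bias". The diet is repeated, supplements are barred, medication and its timing are held constant, and samples are assayed together at the end. These measures reduce drift between day 5 and day 47 but cannot exclude it, for instance through habituation to repeated testing.
4. **The drift values are assumed, and 0.71 is not tied to a named comparison.** Both are true. The estimability result needs neither.
5. **The remedy leaves the bias in Aim 2.** It does: the shift is still 1.5 periods. What changes is that the model is defined and the assumption is visible. Looking at the period 2–3 difference is also a weak check: at n = 28 and two-sided 0.05, power to detect a drift of 0.05, 0.1 or 0.2 is about 6%, 8% and 18%.

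The exact 1.5 also depends on the model. Under the sequence reading with equal variances it is 1.48 or 1.52 at 16/15, and 1.43 or 1.57 at 16/12. None of this alters the conclusion.

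**Conclusion.** The concern holds, and Section 4 must be corrected before analysis. One comparison of six, sit less vs sit, is randomised and can be adjusted for period. The other five are either not estimable or fully confounded with time, depending on how period is read. This follows from the fixed order alone and needs no assumption about drift. The size of any resulting bias is unknown because the documents give neither the amount nor the direction of drift; the error rates above show sensitivity under linear drift and equal variances, not expected harm. The sample size and the sit less vs sit comparison are not in question.

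**What to change.** In Section 4:

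- Replace the period factor with one term on the randomised periods: −1/2 for period 2, +1/2 for period 3, 0 for periods 1 and 4.
- State that sit less vs sit is the only randomised, period-adjusted comparison.
- Report the other five as non-randomised. State that they assume the period 1 and period 4 effects equal the mean of periods 2 and 3 (for control vs exercise, only that periods 1 and 4 are equal), which the data cannot test.
- Show the estimated period 2–3 difference beside them. A clear difference makes the assumption hard to defend; its absence is little reassurance at this sample size.
- Word the Aim 2 conclusion accordingly, and say that 80% power for these five holds only under that assumption.
- As a sensitivity analysis, give the five under a linear period trend. Say that it is the same fit with a different extrapolation and so not independent support. Also give the drift per period that would cancel the observed sit less vs exercise difference (the difference divided by 1.5).

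The cost is text and some extra reporting for each outcome. Regimen order, visits and sample size do not change, and sit less vs sit loses almost no precision. The real price is a weaker claim for Aim 2, which is all that the design supports.
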